8.3.3 Follow-up of AEs and SAEs

After the initial AE/SAE report, the Investigator is required to proactively follow each subject at subsequent visits/contacts. All SAEs, and non-serious AEs of special interest (as defined in Section 8.3.6), will be followed until resolution, stabilisation, the event is otherwise explained, or the subject is lost to follow-up (as defined in Section 7.3). Further information on follow-up procedures is given in Appendix 4.

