9.4.2 Safety Analyses

All safety analyses will be performed on the Safety Analysis Set.

TEAEs are defined as AEs that first occurred or worsened in severity after the first administration of study treatment and prior to 125 days after the last administration of study treatment.

AEs will be coded using the Medical Dictionary for Regulatory Activities (MedDRA). For each study treatment, numbers of TEAEs and incidence rates will be tabulated by preferred term and system organ class.

TEAEs by maximum severity, TEAEs by relationship to study treatment, SAEs, TEAEs leading to death and TEAEs leading to discontinuation of study treatment will be tabulated for each treatment group. Commonly occurring TEAEs, i.e., those that occur in 5% or more of the subjects in either treatment group, will be summarised using descriptive statistics.

All laboratory test results, vital signs measurements, ECG results, weight and body mass index (BMI) will be summarised for each treatment group using descriptive statistics at each scheduled visit for raw numbers and change from baseline. The incidence of treatment-emergent abnormal laboratory, vital sign and ECG values will also be summarised using descriptive statistics.

visit for raw numbers and change from baseline. The incidence of treatment-emergent abnormal laboratory, vital sign and ECG values will also be summarised using descriptive statistics.

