15.1. ADVERSE EVENTS

Adverse Events (AEs) will be coded using Medical Dictionary for Regulatory Activities (MedDRA) central coding dictionary, Version 21.0.

Treatment emergent adverse events (TEAEs) are defined as AEs that started on or after the first dose of study medication and prior to the last date of study medication + 125 days (inclusive).

See 17 for handling of partial dates for AEs. In the case where it is not possible to define an AE as treatment emergent or not, the AE will be classified by the worst case; i.e. treatment emergent. An overall summary of number of subjects within each of the categories described in the subsection below, will be provided as specified in the templates. Listings will include TEAEs and Non-TEAEs.

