16. DATA NOT SUMMARIZED OR PRESENTED

The other variables and/or domains not summarized or presented are:

• Comments

These domains and/or variables will not be summarized or presented but will be available in the clinical study database.

Document: x:\biostatistics\documentation\sap\pya18238_izana_izn-101_sap_v1_0_2019050.docx

Author:

Version Number: 1.0 Version Date: 07May2019 Reference: CS_WI_BS00

Template No.: CS_TP_BS016 Revision 5

Effective Date: 01Apr2018

17. **PARTIAL DATE CONVENTIONS**

Imputed dates will NOT be presented in the listings.

ALGORITHM FOR TREATMENT EMERGENCE OF ADVERSE EVENTS:

START DATE	STOP DATE	ACTION
Known	Known	If start date < study med start date, then not TEAE If start date >= study med start date up to 125 after study med stop date, then TEAE
	Partial	If start date < study med start date, then not TEAE If start date >= study med start date up to 125 after study med stop date, then TEAE
	Missing	If start date < study med start date, then not TEAE If start date >= study med start date up to 125 after study med stop date, then TEAE
Partial, but known components show that it cannot be on or after study med start date	Known	Not TEAE
	Partial	Not TEAE
	Missing	Not TEAE
Partial, could be on or after study med start date	Known	If stop date < study med start date, then not TEAE If stop date >= study med start date up to 125 after study med stop date, then TEAE
	Partial	Impute stop date as latest possible date (i.e. last day

Document: x:\biostatistics\documentation\sap\pya18238_izana_izn-101_sap_v1_0_2019050.docx

Author:

Version Number: Version Date: 07May2019 Reference: CS_WI_BS00

1.0

Template No.: CS_TP_BS016 Revision 5

Effective Date: 01Apr2018

Page 34 of 36

	-	
START DATE	STOP	ACTION
	DATE	
		of month if day unknown or 31st December if day
		and month are unknown), then:
		If stop date < study med start date, then not TEAE
		If stop date >= study med start date, then TEAE
	Missing	Assumed TEAE
Missing	Known	If stop date < study med start date, then not TEAE
Missing	Known	If stop date < study med start date, then not TEAE If stop date >= study med start date, then TEAE
Missing	Known Partial	If stop date < study med start date, then not TEAE If stop date >= study med start date, then TEAE Impute stop date as latest possible date (i.e. last day

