Missing	Known Partial	If stop date < study med start date, then not TEAE If stop date >= study med start date, then TEAE Impute stop date as latest possible date (i.e. last day of month if day unknown or 31st December if day and month are unknown), then:
Missing	Known Partial	If stop date < study med start date, then not TEAE If stop date >= study med start date, then TEAE Impute stop date as latest possible date (i.e. last day of month if day unknown or 31st December if day and month are unknown), then: If stop date < study med start date, then not TEAE
Missing	Known Partial	If stop date < study med start date, then not TEAE If stop date >= study med start date, then TEAE Impute stop date as latest possible date (i.e. last day of month if day unknown or 31st December if day and month are unknown), then: If stop date < study med start date, then not TEAE If stop date >= study med start date, then TEAE

ALGORITHM FOR PRIOR / CONCOMITANT MEDICATIONS:

START DATE	STOP DATE	ACTION
Known	Known	If stop date < study med start date, assign as prior If stop date >= study med start date and start date <= end of treatment, assign as concomitant If stop date >= study med start date and start date > end of treatment, assign as post study

Document:	x:\biostatistics\documentation\sap\pya18238_izana_ izn-101_sap_v1_0_2019050.docx		
Author:		Version Number:	1.0
		Version Date:	07May2019
Template No.	CS_TP_BS016 Revision 5	Reference: CS_WI	_BS00

Effective Date: 01Apr2018

Page 35 of 36

START DATE	STOP DATE	ACTION
	Partial	Impute stop date as latest possible date (i.e. last day of month if day unknown or 31st December if day and month are unknown), then: If stop date < study med start date, assign as prior If stop date >= study med start date and start date <= end of treatment +14 days, assign as concomitant If stop date >= study med start date and start date > end of treatment + 14 days, assign as post treatment
	Missing	If stop date is missing could never be assumed a prior medication If start date <= end of treatment, assign as concomitant If start date > end of treatment, assign as post treatment

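### For adverse events with a partial start date and a known stop date, SAP Section 17 tests the 125-day TEAE limit on the stop date instead of the start date

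*SAP*

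**What the plan says.** SAP 15.1 defines TEAEs as "AEs that started on or after the first dose of study medication" and no later than 125 days after the last dose. Protocol 9.4.2 also looks at onset or worsening, and counts events if they "first occurred or worsened in severity after the first administration of study treatment and prior to 125 days after the last administration". SAP 15.1 then refers to Section 17 for partial dates and adds that, where treatment emergence cannot be decided, "the AE will be classified by the worst case; i.e. treatment emergent".

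The Section 17 table for treatment emergence works row by row:

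- **Known start, any stop:** "If start date >= study med start date up to 125 after study med stop date, then TEAE". The limit is on the start date.
- **Partial start that could be on or after first dose, known stop:** not a TEAE if the stop precedes first dose; otherwise "If stop date >= study med start date up to 125 after study med stop date, then TEAE". The limit is on the stop date, and nothing is said about a later stop.
- **Same partial start, partial stop:** the stop is imputed as the latest possible date, then "If stop date >= study med start date, then TEAE". There is no upper limit.
- **Same partial start, missing stop:** assumed to be a TEAE.
- **Missing start, known or partial stop:** a TEAE if the stop is on or after first dose. There is no upper limit.

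**The concern.** Whether an event is treatment-emergent depends on when it began. A stop date inside the limit does show that the start was inside it too, so the cell's positive branch does no harm. The converse fails: a stop after the limit says nothing about whether the start was late. The cell therefore gives no TEAE class to a long-lasting event that began on treatment. The same event would be a TEAE if its stop date were partial or missing, or if its start date were wholly unknown. Recording more about the event makes it less likely to be counted.

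The TEAE flag drives the tables by system organ class and preferred term, by severity and by relationship, and the summaries of serious TEAEs and of events of special interest (SAP 15.1.1 to 15.1.5). Protocol 8.3.3 says that SAEs and non-serious events of special interest "will be followed until resolution, stabilisation, the event is otherwise explained", so late known stop dates can occur among the events of most interest.

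**Working it through.** This is a date rule, so the check is to run one event through each row.

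**Inputs.** Doses on Days 1, 15, 43 and 71, with ± 2 days on all but the first, and the follow-up visit on Day 197 ± 4 (Protocol 1.3). Follow-up 16 weeks after the End of Treatment visit (Protocol 4.1). Limit of 125 days after last dose (SAP 15.1 and 17).

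**Limit for a full-course subject.** 71 + 125 = Day 196.

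**Classification from the Section 17 table alone** (first dose Day 1, last dose Day 71):

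| Start date | Stop date | Stop on Day 150 or 196 | Stop on Day 197, 201 or 220 |
|---|---|---|---|
| Known, Day 60 | Known | TEAE | TEAE |
| Partial, could be on or after first dose | Known | TEAE | no branch |
| Partial, could be on or after first dose | Partial (latest possible day as shown) | TEAE | TEAE |
| Missing | Known | TEAE | TEAE |

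A partial start with a missing stop is a TEAE without condition.

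**Example (illustrative dates).** First dose 7 January 2019, last dose 18 March (Day 71), limit 21 July (Day 196). An event recorded as starting in April 2019 and stopping on 25 July (Day 200) can only have started between Day 85 and Day 114. Every possible start is inside the window, so it is a TEAE under SAP 15.1. The Section 17 cell does not make it one.

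**How many days are exposed, full course.** Nominally 197 − 196 = 1 day. With the fourth dose on Day 69 the limit is Day 194, and a visit on Day 201 is 7 days past it. With the fourth dose on Day 73 the limit is Day 198, and a visit on Day 193 is 5 days before it.

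**How many days are exposed, earlier last dose.** This depends on when follow-up takes place, so two assumptions are shown.

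| Last dose | Limit | Follow-up kept at Day 197 | Follow-up at early termination visit + 112 days |
|---|---|---|---|
| Day 43 | Day 168 | 29 days | visit Day 71: 183 − 168 = 15 days |
| Day 15 | Day 140 | 57 days | visit Day 43: 155 − 140 = 15 days |
| Day 1 | Day 126 | 71 days | visit Day 43: 155 − 126 = 29 days; visit Day 15: 127 − 126 = 1 day |

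Under the second assumption, an early termination visit within 13 days of the last dose leaves no gap (13 + 112 = 125).

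**Comparison within Section 17.** For a partial start with a known stop, the medication table imputes the earliest possible start and tests that start against its own post-treatment limit. The adverse event table does not.

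**The case against.** The strongest reply is that the SAP already deals with the gap. Right after pointing to Section 17, SAP 15.1 says that an event that cannot be classified is treatment-emergent. A reader might infer that these events get no class anywhere in the plan, or that the plan means to exclude them. The documents do not support that: on its plain reading, 15.1 catches what the table leaves open. This lowers the risk but does not remove it. The known-start rows are also silent beyond 125 days, and there silence must mean not a TEAE. A programmer who reads this cell the same way never reaches the fallback.

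Other inferences also go too far:

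- **All partial start dates are affected.** Only a partial start with a known stop is. Ongoing events and events with a partial stop date are TEAEs.
- **Early stoppers have 29 to 71 exposed days.** Those figures need the final visit to stay at Day 197. Footnote 2 of the Schedule of Activities sends subjects who leave before End of Treatment to the early termination visit and then the follow-up schedule. If follow-up is counted from that visit, the gap is shorter or absent.
- **The effect is 16.7 percentage points.** That is 1/6, the weight of any one of the 6 planned placebo subjects; one of 36 active subjects is 2.8 points. Neither measures this defect, and SAP 15 plans no statistical comparison of safety data.
- **SAEs would disappear from the report.** Listings cover all randomised subjects and include non-TEAEs, and details of SAEs and events of special interest are listed separately. Nor do the documents show that such events would have partial start dates; SAEs are reported within 24 hours (Protocol 8.3.1).

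**Conclusion.** The point stands as a wording error in one cell. For a partial start with a known stop, Section 17 windows the wrong date, contrary to SAP 15.1 and to its own neighbouring rows. As written, the SAP supports two answers for the same event: a TEAE through 15.1, or not a TEAE (or a blank flag) through the table.

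The practical size is small. An event must have an incomplete start date and also a recorded stop later than 125 days after the last dose. For a full-course subject that is 1 day of scheduled follow-up nominally and at most 7 within the visit windows. More is possible after an early last dose, or where an SAE or event of special interest is followed to resolution. How much more depends on follow-up timing and on how often start dates are incomplete, which the documents do not give. An affected event would be lost from summary tables but not from the listings.

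**What to change.** In the cell for a partial start with a known stop, replace the limited rule with "If stop date >= study med start date, then TEAE", as the adjacent rows have it. Restate in Section 17 that any event with a partial or missing start date that the table leaves unclassified is a TEAE under 15.1. Keep that sentence to partial and missing starts: applied to every row, it would turn known starts after the limit into TEAEs. An explicit not-TEAE branch for those known late starts would remove the ambiguity.

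This simple rule also counts an event whose known date components place its start wholly after the window, as the adjacent rows already do. If a post-dose limit is wanted for partial starts, test it on the earliest possible start date in all the partial-start rows, following the medication table. That is a separate and slightly larger change; the two rules should not be mixed.

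The simple version costs a few words in the SAP and about one line of code. It needs no new data, and it should be made before unblinding so that no event has to be classified by judgement afterwards.

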12. MEDICATIONS

Medications will be presented for the SAF and coded using WHO Drug Dictionary Version Dictionary B3 format version March 2018.

See 17 for handling of partial dates for medications, in the case where it is not possible to define a medication as prior, concomitant, or post treatment, the medication will be classified by the worst case; i.e. concomitant.

- 'Prior' medications are medications which started and stopped prior to the first dose of study medication.
- 'Concomitant' medications are medications which:
 - started prior to, on or after the first dose of study medication and started no later than 14 days following last dose of study medication,
 - AND ended on or after the date of first dose of study medication or were ongoing at the end of the study.
- 'Post' medications are medications which started more than 14 days following the last dose of study medication.
- Incidence of prior, concomitant and post medications will be presented by ATC Level 4 code and Preferred Term (PT).

Reference: CS WI BS00

Document:	x:\biostatistics\documentation\sap\pya18238_izana_ izn-101_sap_v1_0_2019050.docx		
Author:	Version Number:	1.0	
	Version Date:	07Mav2019	

Template No.: CS_TP_BS016 Revision 5

Effective Date: 01Apr2018

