13. STUDY MEDICATION EXPOSURE

Exposure to study medication, expressed as number of subjects who received their 1st, 2nd, 3rd and 4th injections, and duration of exposure, will be presented for the SAF.

The date of first study medication administration will be taken from the eCRF "Subcutaneous dosing of IMP" form. The date of last study medication will be taken from the eCRF "End of Treatment" form.

Interruptions, compliance, and dose changes will not be taken into account for duration of exposure.

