Partial	Known	Impute start date as earliest possible date (i.e. first day of month if day unknown or 1st January if day and month are unknown), then: If stop date < study med start date, assign as prior If stop date >= study med start date and start date <= end of treatment + 14 days, assign as concomitant If stop date >= study med start date and start date > end of treatment + 14 days, assign as post treatment

Document: x:\biostatistics\documentation\sap\pya18238_izana_izn-101_sap_v1_0_2019050.docx

Author:

Version Number: 1.0 Version Date: 07May2019 Reference: CS_WI_BS00

Template No.: CS_TP_BS016 Revision 5

Effective Date: 01Apr2018

Page 36 of 36

START DATE	STOP DATE	ACTION
	Partial	Impute start date as earliest possible date (i.e. first day of month if day unknown or 1st January if day and month are unknown) and impute stop date as latest possible date (i.e. last day of month if day unknown or 31st December if day and month are unknown), then: If stop date < study med start date, assign as prior If stop date >= study med start date and start date <= end of treatment + 14 days, assign as concomitant If stop date >= study med start date and start date > end of treatment + 14 days, assign as post treatment
	Missing	Impute start date as earliest possible date (i.e. first day of month if day unknown or 1st January if day and month are unknown), then: If stop date is missing could never be assumed a prior medication If start date <= end of treatment +14 days, assign as concomitant If start date > end of treatment + 14 days, assign as post treatment
Missing	Known	If stop date < study med start date, assign as prior If stop date >= study med start date, assign as concomitant Cannot be assigned as 'post treatment'
	Partial	Impute stop date as latest possible date (i.e. last day of month if day unknown or 31st December if day and month are unknown), then: If stop date < study med start date, assign as prior If stop date >= study med start date, assign as concomitant Cannot be assigned as 'post treatment'
	Missing	Assign as concomitant

 Document:
 x:\biostatistics\documentation\sap\pya18238_izana_izn-101_sap_v1_0_2019050.docx

 Author:
 Version Number:
 1.0

 Version Date:
 07May2019

 Template No.:
 CS_TP_BS016 Revision 5
 Reference:
 CS_WI_BS00

Effective Date: 01Apr2018

Statistical Analysis Plan - v1.0 - SAP - 29-May-2019

Electronic Signature Manifestation

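### SAP Section 17 applies two start-date cut-offs for concomitant medication, 14 days apart, and one of them must contradict Section 12

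*SAP*

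**What the plan says.** SAP Section 12 (Medications) gives the definition. A drug is concomitant if, among other conditions, it "started no later than 14 days following last dose of study medication". A drug that starts later than that is post. The section refers to Section 17 for partial dates, and sends any drug that cannot be classified to the concomitant group.

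The prior/concomitant algorithm in SAP Section 17 (Partial Date Conventions) has one row per combination of start and stop date:

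- **Start known, stop known:** "If stop date >= study med start date and start date <= end of treatment, assign as concomitant". The companion line is "If stop date >= study med start date and start date > end of treatment, assign as post study".
- **Start known, stop missing:** "If start date <= end of treatment, assign as concomitant".
- **Start known, stop partial, and every row with a partial start:** the limit is 14 days later. The partial-start, known-stop row, for example, has "start date <= end of treatment + 14 days, assign as concomitant".
- **Start missing:** no start-date limit. The drug is prior or concomitant and never post.

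Section 17 does not say which date end of treatment is. Two places bear on it. SAP Section 13 takes the last-dose date from the eCRF form named End of Treatment. The protocol (Section 4.1 and the Schedule of Activities) uses End of Treatment as the name of the Week 12 visit.

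**The concern.** Section 12 separates concomitant from post by the start date alone. Three rows of the Section 17 table have a fully known start date, so they should share one limit. They do not: the limit depends on how complete the stop date is. Two drugs started on the same day can therefore land in different tables because one stop date is partial and the other is complete or missing.

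The pattern does not look like deliberate caution about uncertain dates. A missing stop date carries less information than a partial one, yet it gets the narrower window. If ongoing drugs are recorded with no stop date (an assumption about the eCRF), they fall in the narrow row, and complete dates certainly do. The discrepancy therefore reaches ordinary records.

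At stake is whether the concomitant and post medication tables show what Section 12 says they show.

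**Working it through.** **Inputs**

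- Planned injections on Days 1, 15, 43 and 71 (protocol Section 6.2.2), so the planned last dose is Day 71.
- Week 12 visit on Day 85. The Week 10 and Week 12 visits each have a window of ±2 days (protocol Schedule of Activities).
- Section 12 limit: last dose + 14 = 71 + 14 = Day 85.

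The plan gives no figure to reproduce. The check puts the latest start day still called concomitant side by side for each row, under both readings of end of treatment (EoT).

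| Rule (start / stop) | Limit as written | EoT = last dose, Day 71 | EoT = Week 12 visit, Day 85 |
|---|---|---|---|
| Section 12 | last dose + 14 | 85 | 85 |
| Known / known | EoT | 71 | 85 |
| Known / missing | EoT | 71 | 85 |
| Known / partial | EoT + 14 | 85 | 99 |
| Partial / any | EoT + 14 | 85 | 99 |
| Missing / any | none | not applicable | not applicable |

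**Reading 1, last dose.** The known/known and known/missing rows disagree with Section 12 on start Days 72 to 85: 85 − 71 = 14 days. The other rows agree with it. A drug started on Day 75 is post with a known or missing stop date, and concomitant with a partial stop date or under Section 12.

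**Reading 2, Week 12 visit.** The known/known and known/missing rows agree with Section 12 on the planned schedule. The + 14 rows run to 85 + 14 = Day 99 and disagree on Days 86 to 99: 99 − 85 = 14 days. A drug started on Day 90 is post under Section 12 and in the known/known row, but concomitant with a partial stop date.

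**Visit windows.** The gap from last dose to Week 12 runs from 83 − 73 = 10 to 87 − 69 = 18 days. Under Reading 2 even the known/known row can therefore differ from Section 12 by up to 4 days in either direction (10 − 14 = −4; 18 − 14 = +4).

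**Which reading is better supported.** Only under Reading 1 do the + 14 rows reproduce Section 12, and Section 13 ties the last-dose date to the End of Treatment form. Reading 2 has the protocol's name for the visit behind it, so the term is not settled.

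**After correction.** With end of treatment defined as last dose and 14 days added to the two rows, every row that has a start date to compare cuts off at Day 85. Disagreement with Section 12 falls from 14 start days to 0.

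**The case against.** The best defence is that Section 12 is the definition and refers to Section 17 only for partial dates, so complete dates are governed by the 14-day rule whatever the table says. This does not clear the table. Section 17 states an explicit rule for complete dates that a programmer would implement, and a known start with a missing stop is an incomplete-date case by any account.

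A reader might infer that the plan hides new steroid, NSAID or opioid use in the two weeks before the primary assessment. The documents do not support that, for four reasons:

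- The Days 72 to 85 effect exists only if end of treatment means the last dose. If it means the Week 12 visit, the error falls after the endpoint.
- An affected drug moves to another table and is not lost. Section 12 also tabulates post medications, the protocol (Section 9.4) lists individual data, and SAP Section 6.1 puts the study day in every listing that carries an event date.
- Use of an excluded medication under protocol Appendix 5 is recorded as a protocol violation. SAP Section 9 presents deviations for all randomised subjects. That route does not depend on the prior/concomitant/post label.
- The ASAS20 derivation, the non-responder rule and the Bayesian analysis (SAP Section 14.1) do not use the class.

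A reader might also quote longer affected periods. Late visits can leave 18 days between last dose and Week 12. A subject whose last dose was Day 15 but who was still assessed on Day 85 would have Days 30 to 85 (56 days) called post. Both figures follow from Section 12's choice of the last dose as anchor, which is clearly stated. The Section 17 omission accounts for 14 days and no more.

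**Conclusion.** The SAP is wrong as written, and the error is minor. Section 17 uses two limits 14 days apart for the same classification and leaves the anchor date undefined. Under either reading some rows contradict Section 12: Days 72 to 85 in two rows if the anchor is the last dose, or Days 86 to 99 in the + 14 rows if it is the Week 12 visit. The day numbers assume the planned schedule with all four doses given.

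The consequence is limited to the descriptive prior, concomitant and post medication tables on the safety set. The documents give no basis for estimating how many drugs start in the affected days. If the tables are split by arm, which Section 12 does not state, one reclassified subject would shift a placebo incidence by 1/6, about 17 percentage points, and a namilumab incidence by 1/36, about 3 points, at the planned arm sizes. No efficacy result changes.

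**What to change.** In SAP Section 17:

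1. Define end of treatment as the date of last dose.
2. Add 14 days to the limit in the known/known and known/missing rows, in both the concomitant and the post lines.
3. Use one label for post throughout. The known/known row now says post study where the other rows say post treatment.
4. Leave the missing-start rows as they are, because they have no start date to compare with a limit.

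Optionally, move the concomitant limit in both Section 12 and Section 17 to the later of last dose + 14 days and the Week 12 or early-termination assessment date. That would cover late visits and missed doses. It changes the definition and goes beyond correcting the inconsistency, so it is a separate choice.

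The cost is a few words of SAP text and the matching program lines. No new data are needed.
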